5.2.1 Brief Description of the Investigational Product

SA (also known as N-acetylneurameric acid or NANA) intended as a substrate replacement therapy for GNE Myopathy, which is caused by a defect in the de novo biosynthesis of sialic acid. The choice of an extended release formulation is based on the fact that SA has a short half-life in the circulation and its rapid clearance makes it difficult to use as a therapeutic replacement substrate in which a steady and constant supply of SA is needed. SA-ER was developed to improve the stability of exposure to SA and allow more appropriate dosing and efficient substrate replacement.

SA-ER 500 mg tablets are white to off-white, uncoated or film-coated, extended release, oval tablets that are designed for oral administration. The tablet formulation contains approximately 43.3% active pharmaceutical ingredient in a mixed polymer matrix developed for extended release of SA over 24 hours. Tablets are manufactured by a formulation process using wet aqueous granulation; the blend is then dried and compressed into tablets. Film-coated tablets are coated with Opadry II, a non-functional aqueous film coating. SA-ER 500 mg tablets are 1,150 mg in total weight.

Since successful use of SA replacement therapy in humans is believed to depend upon optimized exposure to the compound, an increased dose was examined in Part II of this extension study. Although administration of more extended release tablets could have been utilized, data in canines suggested that administration of immediate release SA in

combination with the SA-ER would maximize absorption in the GI tract. Therefore a study testing an increased dose level combining immediate release SA (SA-IR) with SA-ER was proposed in Amendment 1. Amendment 2 allows for subjects to receive either 6g/day or 12g/day based on the data collected and analyzed from Part II. Refer to Section 7.2 for additional details and rationale for the dose reduction in Part III.

SA-IR 500mg capsules are naturally colored, size 000, immediate release, hard gelatin capsules designed for oral administration. The capsule formulation contains approximately 93.5% active pharmaceutical ingredient. Manufacturing consists of dry blending followed by filling into capsules. SA-IR capsules have a fill weight of approximately 535 mg and a total weight of approximately 698 mg.

5.2.2 Nonclinical Studies

Published in vivo studies in the HIBM mouse model have shown that replacement by SA can reduce muscle weakness and atrophy, improve muscle pathology and function, and restore sialylation in muscle (Malicdan et al. 2009). The rational basis for the use of SA as a therapy in GNE Myopathy is primarily dependent on these results. Key safety pharmacology, PK, and toxicology studies to support the use of SA in treating GNE Myopathy are summarized below; additional details may be found in the IB.

Safety pharmacology: Ultragenyx conducted the core battery of safety pharmacology studies of SA that are recommended by ICH guidelines. These studies consisted of in vitro human ether-à-go-go-related gene (hERG) channel inhibition, neurobehavior in rats, and respiratory and cardiovascular evaluations in dogs after oral administration of SA. SA did not show any potential for QT prolongation in the hERG assay at concentrations as high as 6×10^{-3} mole/L. There were no adverse effects on neurobehavior in rats or on respiratory and cardiovascular function in dogs at oral SA doses as high as 2000 mg/kg.

PK study in dogs: Ultragenyx conducted a multiple-dose, cumulative dosing, PK study in dogs to assess exposure following administration of SA-ER and the SA-ER/SA-IR treatment combination. Each dog was administered SA-ER (200 mg/kg/day; human dose equivalent 100 mg/kg/day) TID throughout the study duration (12 days). Following 4 days of SA-ER treatment, SA-IR (100 mg/kg/day) TID was added to SA-ER treatment. Following 4 days of SA-ER/SA-IR treatment, the SA-IR dose was increased to 200 mg/kg/day. The highest dose level of SA-ER/SA-IR was equivalent to a human dose of 200 mg/kg/day. The area under the curve (AUC) during the 8-hr dosing window increased proportionally to the dose of SA-IR, suggesting the administration of SA in extended-release and immediate-release forms can improve overall absorption of SA-ER and increase free SA levels up to 3X in the serum. Overall SA-ER/SA-IR was well tolerated in this study.

Chronic toxicology studies in rats and dogs: In an oral 6-month rat study, there were no treatment-related effects on clinical condition, body weight, food consumption, ophthalmology, clinical pathology (hematology, blood chemistry, and urinalysis) and in pathologic evaluations (gross, organ weight, and histopathology). The no observed adverse

effect level (NOAEL) in this study was 2000 mg/kg which is equivalent to approximately a 17 g daily human dose. This provides a safety margin of approximately 1.4-fold over the proposed highest dose (12g/day) in the Phase 2 UX001-CL201 Study. The 9-month oral toxicity study in dogs did not show any adverse effects on clinical condition, body weight, food consumption ophthalmology, electrocardiography, clinical pathology (hematology, blood chemistry, and urinalysis) and in pathologic evaluations (gross, organ weight, and histopathology). The NOAEL in this study was 2000 mg/kg which is equivalent to a 60 g daily human dose. This provides a safety margin of approximately 5-fold over the proposed highest dose (12g/day) proposed in the Phase 2 UX001-CL201 Study.

Reproductive and developmental toxicology studies in rats and rabbits: To date, reproductive and developmental toxicity studies at oral doses as high as 2000 mg/kg/day have not shown any adverse effects on fertility of male or female rats, or treatment-related effects on pregnant females or embryo-fetal development parameters in rats and rabbits.

5.2.3 Previous Clinical Studies

Key results from studies to support the use of SA in treating GNE Myopathy are summarized below; additional details may be found in the IB.

Phase 1 PK and Safety (UX001-CL101): “A Phase 1 Study to Evaluate the Safety and Pharmacokinetics of Single and Repeat Doses of Sialic Acid Extended-Release (SA-ER) Tablets in Patients with Hereditary Inclusion Body Myopathy (HIBM) ”.

The study was conducted in 28 subjects who received single and multiple doses to assess the PK and safety of SA-ER. Subjects received SA-ER tablets orally at one of five dose levels in the single dose phase, and one of four levels in the repeat dose phase. Each of the 28 enrolled subjects were sequentially assigned to a specific dose level and received two single-dose exposures at that same dose level (fasted and fed). The low dose cohorts were filled before assigning higher dose cohorts. The subjects were then assigned to receive one repeat-dose regimen. The lower dose repeat-dose cohorts are being filled before proceeding to higher repeat-dose levels. Dose levels are as follows:

- *single doses:* 650 mg (n = 6), 1,950 mg (n = 6), 2,925 mg (n = 6), 4,875 mg (n = 4), 6000 mg (n=6).
- *multiple dosing:* 650 mg TID (1,950 mg/day; n = 8), 975 mg TID (2,925 mg/day; n = 8), 1,625 mg TID (4,875 mg/day; n = 6), 2000 mg TID (6000 mg/day; n = 6).

Safety evaluations have not shown any significant drug-associated safety problems. Preliminary PK analyses show that the drug is absorbed with some variation in humans. Multi-day dosing has shown increased and sustained blood levels of free SA over a 24 hour cycle, consistent with expectations for an extended release formulation.

Phase 2 PK, PD and Safety (UX001-CL201): “A Phase 2 Randomized, Double-Blind, Placebo-Controlled, Parallel Group Study to Evaluate the Dose and Pharmacodynamic Efficacy of Sialic Acid-Extended Release (SA-ER) Tablets in Patients with GNE Myopathy or Hereditary Inclusion Body Myopathy”.

A Phase 2 randomized, placebo-controlled study has been performed to evaluate the safety and PD effects of SA-ER at two dose levels (3g and 6g/day). The study consists of a 24-week placebo-controlled Treatment Period, followed by an additional 24-week Treatment Continuation Period whereby all subjects receive active treatment. A planned analysis was conducted following completion of the 24-week placebo-controlled Treatment Period; the goal was to identify the dose that provides the best risk-benefit profile.

Results of planned PK, PD, clinical efficacy, and safety analyses following the 24-week placebo-controlled Treatment Period showed dose-dependent improvement in muscle strength relative to placebo, particularly in the upper extremities at the 6g SA-ER dose. These changes were statistically significant or trended towards significance, and were more pronounced in subjects that had greater walking ability at baseline, a predefined subset. Other clinical endpoints did not reveal changes at this Week 24 interim assessment. CK levels showed a trend to improvement in the 6g SA-ER dose group compared with placebo. SA-ER appeared to be well tolerated with no serious adverse events (SAEs) observed in either dose group. As expected, the highest dose (6g/day SA-ER) provided a sustained exposure, a clinical efficacy signal, and acceptable safety profile.

GNE Myopathy-Disease Monitoring Program: A natural history study collecting data on the disease characteristics and its progression is also in progress.

5.3 Summary of Overall Risks and Potential Benefits

Since SA is a normal body compound with native pathways for degradative metabolism and rapid renal clearance, there is no evidence or expectation of a significant safety issue with SA replacement therapy at this time. Data from nonclinical and clinical studies to date suggest SA-ER administered alone or with SA-IR does not pose any significant safety risks that can be identified at this time. Toxicology or adverse pharmacology findings were not observed in SA-treated animals; at very high doses, osmotic diarrhea may be observed in treated dogs. Interim safety results following a 24-week Treatment Period in a completed Phase 2 study (UX001-CL201), suggested an increase in diarrhea and GI symptoms relative to placebo. No correlation was observed between the GI events and free SA serum levels suggesting the frequency of GI events does not appear to be dose dependent.

In patients with GNE Myopathy, replacement of the substrate SA has the potential to restore normal sialylation of muscle glycoproteins and glycolipids, which could improve the function of muscle and limit the loss of muscle strength. It is not clear how much the effects of GNE Myopathy are reversible or if and how fast reversal of muscle disease might occur. The data in the HIBM mouse model suggest that over a one year period, substantial beneficial effects on the pathology of the disease are possible. However, it is not clear

whether advanced disease can improve, as opposed to preventing progression of existing disease. If the therapy has an effect comparable to that observed by Sparks and colleagues using intravenous immune globulin (IVIG) as a source of SA ([Sparks et al. 2007](#)), then the benefit to GNE Myopathy patients in improving muscle strength and function might be substantial. In clinical studies conducted to date, the highest dose (6g/day SA-ER) provided a sustained exposure, a clinical efficacy signal, and acceptable safety profile. Overall the risk-benefit ratio appears to be favorable based on the excellent safety record to date, and the potential benefit observed in nonclinical and clinical studies.

5.4 Study Rationale

GNE myopathy or HIBM is a severe progressive metabolic myopathy caused by a defect in the biosynthetic pathway for sialic acid (SA). Substrate replacement of SA is a potential therapeutic strategy based on evidence from relevant in vivo models, supported by PK characterization in a Phase 1 clinical study, and improvement in muscle strength from a Phase 2 randomized controlled trial. The first study showed some efficacy at the 6g dose level but not at 3g, indicating the dose level may be at the low end of the dose response curve. The interim data implied a clinical efficacy signal and acceptable safety profile suggesting the potential to optimize the therapeutic index by increasing SA exposure. Since successful use of SA replacement therapy in humans is believed to depend upon optimized exposure to the compound, an increased dose was suggested. Although administration of more extended release tablets could be utilized, data in canines suggests that administration of immediate release SA (SA-IR) in combination with the SA-ER will maximize absorption in the GI tract. Therefore a study testing an increased dose level combining SA-IR with SA-ER is proposed.

Subjects completing the 48-week UX001-CL201 study are eligible to continue treatment under this open-label extension protocol testing an increased dose of SA. Additional GNE Myopathy subjects will be enrolled to assess the safety and efficacy of SA-ER/SA-IR in a treatment-naïve population. Ultragenyx is conducting this study in four parts: Part I of the study will provide additional information on the long-term safety and efficacy of 6g/day SA-ER; Part II of the study will assess the safety and efficacy of 12g/day of SA (comprised of 1.5 g of SA-ER / 1.5 g of SA-IR treatment QID). Part III of the study reduces the dose from 12g/day to 6g/day for subjects who did not show additional benefit at 12g/day; however, treatment-naïve subjects and a small subset of rollover subjects will be invited to remain on the higher dose of 12g/day (described in Section [7.2](#)). Part IV was added to change the formulation from SA-IR to SA-ER. The SA-IR dose formulation has been removed based on data showing that by the 4th day of dosing in a nonclinical study conducted in dogs, AUC for free SA was similar between the immediate and extended release formulations. In addition, a review of population data for Month 12 of Part III in the current study confirmed that 12g/day SA-IR did not appear to provide any additional benefit compared with 6g/day SA-ER, although some individual patients may have improved. Therefore, no further SA-IR will be administered after the initiation of Part IV; patients currently on 12g/day may continue receiving the 12g/day dose, if desired, by taking SA-ER.

6 STUDY OBJECTIVES

The safety objectives of the study are to:

- Evaluate additional long-term safety of SA-ER treatment of GNE Myopathy subjects previously treated with SA-ER at dose of 6g/day (Part I)
- Evaluate the safety of 12g /day SA (delivered by 1.5g of SA-ER tablets and 1.5g of SA-IR capsules 4 times per day) in the treatment of GNE Myopathy subjects (Part II) over a 6 month treatment period
- Evaluate the safety of SA treatment at both 6g/day and 12 g/day (Part III [SA-ER/SA-IR] and Part IV [SA-ER]).

The clinical objectives of the study are to:

- Evaluate the long-term effect of SA treatment of GNE Myopathy subjects on muscle strength as measured by hand-held dynamometry (HHD)
- Evaluate the long-term effect of SA treatment of GNE Myopathy subjects on mobility, strength, and function using a series of physical performance measures
- Evaluate the long-term effect of SA treatment of GNE Myopathy subjects on functional disability using an interview-based questionnaire.

The exploratory objectives of the study are to:

- Evaluate the effect of SA-ER treatment on serum biomarkers of sialylation in GNE Myopathy subjects (Part I)
- Determine whether 12g/day SA-ER/SA-IR administered 1.5g/1.5g four times per day is superior to prior treatment with SA-ER in GNE Myopathy subjects (Part II)
 - Determine whether a subset of subjects has additional benefit on the higher dose treatment.

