Part III: 12g/day dose – Each dose of SA-ER/SA-IR will consist of SA-ER tablets, each containing 500 mg of SA active ingredient in an extended release formulation and SA-IR capsules, each containing 500 mg of SA active ingredient. During the Part III Treatment Period, the 12,000 mg (12g) total daily SA dose will be administered by the oral route and will be divided into a TID or QID regimen. If tolerability issues arise, the dose may be temporarily stepped down until symptoms resolve.

6g/day dose – Each dose of SA-ER will consist of tablets, each containing 500 mg of SA active ingredient in an extended release formulation. During the Treatment Period, the 6000 mg (6g) total daily SA-ER dose will be administered by the oral route and will be divided into a TID regimen.

Part IV: 6g/day dose and 12g/day dose – Each dose of SA-ER will consist of tablets, each containing 500 mg of SA active ingredient in an extended release formulation. During the Treatment Period, the 6g total daily SA-ER dose will be administered by the oral route and will be divided into a TID

regimen. The 12g total daily SA-ER dose will be administered by the oral route and will be divided into a TID or QID regimen.

All doses should be taken with food (i.e. within 30 minutes following a meal or snack).

DURATION OF TREATMENT:

The Part I Treatment Period will be up to approximately 12 weeks (3 months) in duration. The Part II, Part III, and Part IV Treatment periods will be up to 36 months in duration. The total duration of the study will be up to 40 months.

CRITERIA FOR EVALUATION:

Efficacy:

Efficacy will be evaluated by continued improvement in clinical assessments. Efficacy assessments may differ depending on the phase of the study (i.e. Part I, Part II, Part III, or Part IV). For Part I efficacy evaluation, results from the last pre-treatment assessment from UX001-CL201 will be compared with the last post-treatment assessment for the Part I Treatment Period as listed in the Schedule of Events ([Table 2.1](#)), with efficacy conclusions based on change since SA-ER treatment initiation.

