Safety will be evaluated by the incidence and frequency of AEs and SAEs, including clinically significant changes from Baseline to scheduled time points in:

- Vital signs
- Neurological and physical examination results
- Laboratory evaluations
- Interval history: reported symptoms of increasing muscle weakness or pain, incidence of falls

STATISTICAL METHODS:

Details of the planned interim analysis, safety and efficacy analyses will be provided in a statistical analysis plan maintained separately from this protocol.

Interim Analysis:

An Interim analysis will be conducted when a majority of subjects have completed the Month 6 Visit during the Part II Treatment period.

Efficacy Analyses:

Efficacy data analyses will be conducted at the end of the 6-month Treatment Period with SA-ER/SA-IR, when all subjects have completed 12 months of participation, and at the end of the 36 month Treatment Period. The treatment naïve subjects will be studied as a separate subgroup.

Clinical efficacy analyses will include: 1) Muscle strength as measured by HHD, and reported as force in kg and percent of predicted normal, 2) Walking ability as measured by the 6MWT, and reported as distance in meters and percent of predicted normal, 3) Walking speed as measured by the walking speed test, which will be reported in seconds and percent of predicted normal for each walking speed, 4) Arm raising ability as measured by the weighted arm lift test, which will be reported as the total number of completed repetitions, and 5) Functional disability as measured by the HIBM-FAS, which will be reported as a total score and subscale scores for mobility, self-care, and upper extremity function with lower scores associated with greater disability.

For those clinical evaluations with repeated assessments (i.e., HHD, 6MWT, and the walking speed and weighted arm lift tests), the analysis will be performed using a repeated measures analysis.

A full accounting of the analyses for Parts III and IV of the study will be provided in the Statistical Analysis Plan.

Safety Analyses:

All subjects who receive study drug will be included in the safety analysis. Safety will be evaluated on the incidence and frequency of AEs and SAEs, and clinically significant change in vital signs, laboratory test results, or physical examinations. Safety data will be periodically reviewed by the DMC.

Table 2.1: Schedule of Events (Part I)

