7 INVESTIGATIONAL PLAN

7.1 Overall Study Design and Plan

This open-label extension study will assess the long term safety and efficacy of SA treatment over a period of approximately 36 months, or until marketing approval or program termination by Ultragenyx. In Part I of the study, approximately 46 subjects will be enrolled following successful completion of the UX001-CL201 study. The Baseline visit will be conducted in conjunction with the UX001-CL201 Week 48 study visit to avoid treatment disruption. Enrollment will take place after all UX001-CL201 Week 48 study assessments have been completed and the investigator has determined the subject meets all eligibility criteria. Data collected at the UX001-CL201 Week 48 visit will serve as the Baseline data for Part I of this protocol. Following the signing of informed consent at the Baseline visit, each subject will be dispensed a 6-week supply of study drug. Throughout the Part I Treatment Period of the study, all subjects will continue to take four 500 mg SA-ER tablets orally three times per day (TID), in the morning, early evening, and at bedtime (qHS), for a total dose of 6g/day. The Part I Termination Visit will also serve as the Baseline Visit for Part II of the study.

Beginning with the Part II-Baseline Visit, all subjects currently enrolled in Part I will crossover to the SA-ER/SA-IR dosing regimen. Approximately 10 treatment naïve GNE Myopathy subjects will be enrolled into Part II of the study. The additional subjects will provide an assessment of SA-ER/SA-IR treatment in SA naïve subjects able to walk at least 200 meters (and < 80% predicted) in a screening 6 Minute Walk Test (6MWT). Throughout the 36-month Part II Treatment Period, all subjects will be administered 1.5g SA-ER and 1.5g SA-IR orally four times per day (QID), in the morning, afternoon, early evening, and qHS, for a total SA dose of 12g/day.

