7.2 Discussion of Study Design, Including Choice of Control Group

Part I of the study will focus on evaluating the long-term safety of 6g/day SA-ER treatment in GNE Myopathy subjects continuing SA-ER treatment as an extension of the 48-week, Phase 2 UX001-CL201 clinical study. Part I of the study will also explore long-term effects of SA-ER on clinical measures of muscle strength, mobility, function, disability and health-related quality of life. Exploratory evaluations of the effects of SA-ER on serum biomarkers will be performed in Part I of the study only.

Since Part I of the study is designed as an open-label extension designed to continue SA-ER treatment for subjects successfully completing the Phase 2 UX001-CL201 study, the study size and population are therefore restricted to said individuals. In UX001-CL201, safety and efficacy of SA-ER was examined in a randomized, double-blind study at two dose levels and compared to placebo treatment control. The current study design is not powered to assess statistically significant comparisons between treatment groups. Instead, the study population for Part I is intended to provide additional long-term safety data following maintenance treatment with 6g/day SA-ER. Since all subjects will receive the same treatment, randomization or blinding of study drug is not necessary.

The Week 24 interim data from the Phase 2 UX001-CL201 study implied a positive PD signal and acceptable safety profile suggesting the potential to optimize the therapeutic index by increasing SA exposure. Therefore, investigation into optimizing the risk-benefit profile of SA substrate replacement by examining higher SA doses is warranted. Part II of the study will assess the long-term safety and efficacy of an increased SA dose (total 12g/day) for up to 12 months. In this phase, SA treatment will be in the form of SA-ER tablets and immediate release capsules (SA-IR) to maximize absorption from the GI tract based on data obtained from nonclinical studies in canines. Continuing subjects will terminate Part I of the study

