6.10.1 Adverse Events

Adverse Events will be assessed at all visits and throughout the course of the study. The number and percent of subjects with any treatment-emergent adverse events (TEAEs) will be displayed by system organ class and preferred term for each treatment group (6g/day SA-ER, 12g/day SA-ER/SA-IR). Within each preferred term, subjects will be counted only once if they had more than one event reported during the treatment period. The same summary will be performed for all serious TEAEs and all TEAEs causing discontinuation of study drug.

The number and percent of subject TEAEs will also be summarized by greatest reported severity grade (Grades 1-5) for each event preferred term by treatment group. Wherever possible, the severity of all AEs observed will be graded using the NCI CTCAE (V4.0) as follows in [Table 9](#):

Table 9 NCI-CTCAE Common AE Grading Criteria

Grade	Description
1	Mild; asymptomatic or mild symptoms; clinical or diagnostic observations only; intervention not indicated.
2	Moderate; minimal, local or noninvasive intervention indicated; limiting age-appropriate instrumental ADL*.
3	Severe or medically significant but not immediately life-threatening; hospitalization or prolongation of hospitalization indicated; disabling; limiting self-care ADL**.
4	Life-threatening consequences; urgent intervention indicated.
5	Death related to AE.
Source: Common Terminology Criteria for Adverse Events (CTCAE), Version 4.0, Published May 28, 2009 (v4.03, June 24, 2010); USHHS/NIH/NCI * ADL=Activities for Daily Living: Instrumental ADL refer to preparing meals, shopping for groceries or clothes, using the telephone, managing money, etc. ** Self-care ADL refer to bathing, dressing and undressing, feeding self, using the toilet, taking medications, and not bedridden.	

The majority of AEs and TEAEs can be graded using the NCI-CTCAE system. Wherever possible, the severity of all AEs will be graded using the NCI CTCAE. The majority of AEs can be graded using this system. If an AE cannot be graded using the CTCAE criteria, it should be graded as mild, moderate, severe, life-threatening, or death using the definitions in Table 10.

Table 10 Mapped AE Grading Criteria

Grade	Description
Mild (Grade 1)	Awareness of signs or symptoms, but easily tolerated and of a minor irritant type, causing no loss of time from normal activities. Symptoms do not require therapy or a medical evaluation; signs and symptoms are transient.

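### The Part II safety objective covers 6 months at 12 g/day, but the stated length of Part II varies and the 12 g/day adverse-event percentages have no per-subject cut at Month 6

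*Protocol*

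**What the plan says.** **Length of Part II in current text**

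- Protocol section 6 and the SAP safety objectives (SAP section 2, sub-heading 1.1) set the 12 g/day safety question "in the treatment of GNE Myopathy subjects (Part II) over a 6 month treatment period".
- The statistical methods in the protocol synopsis place an efficacy analysis "at the end of the 6-month Treatment Period with SA-ER/SA-IR", with further analyses at 12 and 36 months.
- Protocol 7.2 describes "an increased SA dose (total 12g/day) for up to 12 months".
- Protocol 7.1 states: "Throughout the 36-month Part II Treatment Period, all subjects will be administered 1.5g SA-ER and 1.5g SA-IR orally four times per day". SAP section 3 says the same.
- The synopsis, under duration of treatment, states: "The Part II, Part III, and Part IV Treatment periods will be up to 36 months in duration". It gives Part I about 12 weeks and the whole study up to 40 months.
- SAP section 1, written against the protocol through Amendment 1, describes 6 months at 12 g/day with possible continuation to 36 months.

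Protocol 7.1 also introduces Part III, which lowers the dose to 6 g/day for subjects without added benefit at the interim analysis. Treatment-naïve subjects and a small subset of rollover subjects may stay on 12 g/day. Table 2.2, footnote b, times the Part III and IV transition visits from IRB/EC approval, so no study month marks the end of Part II.

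**How adverse events are counted**

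- SAP 6.10.1 tabulates number and percent of subjects with treatment-emergent events (TEAEs), "displayed by system organ class and preferred term for each treatment group (6g/day SA-ER, 12g/day SA-ER/SA-IR"), each subject once per preferred term.
- SAP 6.5.3 runs the TEAE window from first dose to 30 days after the final dose.
- SAP 6.3 plans an analysis after 6 months at 12 g/day, in the Safety Population among others, as initial safety information. SAP 6.4 plans the final analysis at about 36 months.
- The synopsis and protocol 7.6.1.1 trigger the interim analysis when a majority of subjects have completed Month 6.

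**The concern.** A percentage of subjects with at least one event rises with follow-up, so it can be read only against a known window. The objective names a 6-month window. The counting rules do not use it, and the inconsistent lengths of Part II give the analyst no other fixed end point. The study is unpowered and safety is summarised descriptively (protocol 7.6.4, SAP 6.10), so these percentages are in effect the safety result. If follow-up differs between subjects at the Month 6 cut, and again between that cut and the final lock, the 12 g/day column does not estimate 6-month risk. A change between the two sets of tables could then reflect longer observation alone.

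**Working it through.** **1. Which reading of 36 months fits the stated total.** Inputs are Part I of 12 weeks, 36 months, and a Termination Visit 4 weeks after the last dose, with a month of 365.25/12 = 30.44 days.

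84/30.44 + 36 + 28/30.44 = 2.76 + 36 + 0.92 = 39.7 months.

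This reproduces the synopsis total of up to 40 months (3 + 36 + 1 in round figures). The total is met with 36 months as the combined length of Parts II, III and IV. If Part II alone took 36 months, 40 − 3 − 36 − 1 = 0 months would remain for Parts III and IV. Protocol 7.1's 36-month Part II with all subjects on 12 g/day also conflicts with the Part III dose reduction described in the same section. The 12 months in protocol 7.2 match neither the 6-month objective nor the 36 months.

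**2. What the Month 6 analysis would count.** At the data cut most subjects are still on treatment, so the final-dose-plus-30-days limit has not been reached and each subject's window stays open to the cut. A majority trigger allows some subjects to have less than 6 months and others more. No rule in SAP 6.3, 6.5.3 or 6.10.1 truncates a subject's events at Month 6. None of the planned TEAE tables (SAP 8.1, Tables 9 to 14) is limited to Months 0 to 6, and no exposure-adjusted rate is planned.

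**3. Size.** The documents give no event rates, enrolment spread or cut date, so this step is illustrative. Assume a constant hazard and let p6 be the proportion with the event by 6 months. Then P(t) = 1 − (1 − p6)^(t/6), with t in months. The 7- and 9-month columns represent an assumed average overrun of 1 and 3 months.

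| p6 | 7 months | 9 months | 12 months | 36 months |
|---|---|---|---|---|
| 5% | 5.8% | 7.4% | 9.8% | 26.5% |
| 10% | 11.6% | 14.6% | 19.0% | 46.9% |
| 20% | 22.9% | 28.4% | 36.0% | 73.8% |

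For p6 = 10%: 1 − 0.9^(7/6) = 0.116; 1 − 0.9^(9/6) = 0.146; 1 − 0.9^2 = 0.190; 1 − 0.9^6 = 0.469.

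The distortion can also run downward. A subject with only 3 months at the cut has 1 − 0.9^(3/6) = 5.1%.

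**4. The neighbouring column.** Part I at 6 g/day lasts about 2.76 months. The same formula gives 1 − 0.9^(2.76/6) = 4.7%. The two dose columns in SAP 6.10.1 would therefore differ under an identical hazard.

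**The case against.** The strongest reply has four parts.

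- **The 6 and 36 months can be read together.** The objective's 6 months is an evaluation horizon, and SAP section 1 describes an initial 6 months followed by possible continuation. This stands in part. It does not account for the 12 months in protocol 7.2, or for a 36-month Part II on 12 g/day alongside Part III.
- **The window is defined and a 6-month safety analysis exists.** A reader might infer that the adverse-event window is wholly unspecified. The documents do not support that: SAP 6.5.3 bounds it, and SAP 6.3 schedules the analysis in the Safety Population, which SAP section 4 allows to be split by Part. What remains is that the bound is specific to each subject and unrelated to Month 6.
- **Nobody says the final table will be called 6-month safety.** This is correct. A cumulative table also serves the long-term objectives for Parts III and IV, all TEAEs are listed by subject, and no section promises that the two sets of tables can be compared. The point is only that no planned table is fixed to the window the objective names.
- **The 36-month figure is remote.** A reader might infer that the reported 6-month percentage could be inflated 4.7-fold (46.9/10). That requires subjects to remain on 12 g/day for 36 months. Part III reduces the dose for subjects without added benefit, and no SA-IR is given once Part IV starts. The 36-month figure is therefore an upper bound for those who stay on 12 g/day throughout.

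**Conclusion.** The point holds in a limited form. The durations given for Part II in current protocol and SAP text conflict and must be reconciled. The Month 6 analysis answers the 6-month safety objective only approximately, because the 12 g/day percentages cover unequal follow-up that is not tied to 6 months. The Month 6 and final tables are not comparable for the same reason.

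The size cannot be fixed from the documents. Under a constant hazard, which they neither state nor contradict, a 10% six-month incidence would read about 12% to 15% if follow-up at the cut ran 1 to 3 months past Month 6 on average, and 19% at 12 months. Short follow-up in late enrollees would pull the other way. The 47% at 36 months marks the extreme and should not be quoted as the expected distortion. This is a low-cost improvement to a descriptive safety analysis. No stated figure in the documents changes.

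**What to change.** 1. Reconcile the length of Part II across the protocol synopsis (duration of treatment and statistical methods), protocol sections 6, 7.1 and 7.2, and SAP section 3. The sponsor must settle which duration applies.
2. In SAP 6.10.1, report the Part II safety objective per subject from first 12 g/day dose to that subject's Month 6 visit, using the same rule at the Month 6 and final analyses. State how subjects who have not reached Month 6 at the cut are handled. The Month 6 visit has a ±14-day window, so a small variation remains.
3. Show events after Month 6 in a separate column by the dose received at onset. The current SAP describes only Parts I and II and has no rule for assigning events in Parts III and IV.
4. Preferably add exposure-adjusted rates, so that the later column and the shorter Part I column can be read alongside the 6-month one.

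The cost is SAP wording and one extra column in the TEAE tables. It uses event and dosing data already collected.
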